6.1.2. Definition of Study Baseline

Unless otherwise specified, for efficacy and health outcome, baseline is defined as the last nonmissing assessment recorded on, or prior to, the date of the first study drug administration at study Day 1. If 2 viral load records exist with identical sample dates and times, the results for the highest viral load will be used in the analysis.

Baseline for safety analysis is described in the safety section.

Change from baseline will be calculated as the visit value of interest minus the baseline value. If a baseline values or the value at the visit is missing for a particular variable, then the change from baseline is defined as missing.

6.1.3. Study Time Intervals

To calculate the length of any time interval or time period in this study, the following formula will be used:

 $Length\ of\ interval\ (days) = End\ Date - Interval\ Start\ Date + 1$

To convert any time length from days to weeks, the following formula will be used:

Length of interval (weeks) = Length of interval (days)/7

Only for the purpose of calculating the length of study period time intervals, the words "prior to" in Table PYAH.6.2 should be understood to mean "the day before" while the words "after" should be understood to mean "the day after." For the purpose of determining whether a date/time lies within an interval, these words are intended to convey whether the start or end of the period is inclusive of the specified date.

Study Period	Interval Start Definition	Interval End Definition
Screening: All participants who sign informed consent are considered as entering the Screening Period.	Informed consent date	Prior to the start of Treatment and Assessment Period.
Treatment and Assessment Period: All participants who are randomized to the study are considered as entering the treatment and assessment period.	At the start of study drug administration date/time following randomization. For participants who are randomized but not dosed, the treatment and assessment period starts on the date of randomization.	The minimum of treatment and assessment period discontinued date, study discontinuation date, or first post treatment follow-up visit date.
Post-Treatment Follow-Up: All participants who had a follow up visit are considered as entering follow-up period.	After the Treatment and Assessment Period ends.	The maximum of the last study visit date or study disposition date.

Table PYAH.6.2. Definition of Study Period Time Intervals

6.1.4. Analysis Methods

Unless otherwise specified, variables will be analyzed in the original scale on which they are measured. SARS-CoV-2 viral load data will be evaluated in log base 10 scale. The parametric approach will be employed by default for statistical analysis except when nonparametric analysis, such as by a rank-based method, Mann-Whitney, or van Elteren tests, is deemed to be more appropriate.

All hypothesis tests will be 2-sided at an alpha level of 0.05. No adjustment for multiplicity will be performed for Treatment Arms 1-8. For Treatment Arms 9-11, a hierarchical multiple comparisons procedure, which will control type I error in the primary endpoint analysis, will be implemented, see Section 6.5.

Any change to the data analysis methods described in the protocol will require an amendment only if it changes a principal feature of the protocol. Additional exploratory analyses of the data may be conducted as deemed appropriate, including pharmacokinetic/pharmacodynamic (PK/PD) model-based exposure-response analyses.

Table PYAH.6.3. Tables and Figures Related to Demographics and Other Characteristics of Study Population

Method	Analysis
Descriptive Statistics	Number of participants, mean, standard deviation, median, minimum, and maximum for continuous measures, and frequency counts and percentages for categorical measures
Kaplan-Meier curves and summary statistics, Cox proportional hazards	Treatment comparisons of time-to-event based endpoints
Logistic regression analysis	Treatment comparisons of binary variables with treatment in the model
Nonparametric	Treatment comparison of ordinal, nominal, and non-

(e.g., Mann-Whitney or van Elteren tests)	normally distributed continuous variables
Mixed-effects model repeated measures (MMRM)	Treatment comparisons of continuous efficacy and
analysis	health outcome variables

Treatment comparisons of continuous efficacy, and pharmacodynamic variables with multiple postbaseline measurements will be made using a mixed-effects model repeated measures (MMRM) analysis. When MMRM is used, it includes: (a) treatment group, (b) baseline value in the model, (c) visit, and (d) the interactions of treatment-by-visit as fixed factors. The covariance structure to model the within-patient errors will be unstructured. If the unstructured covariance matrix results in a lack of convergence, the heterogeneous Toeplitz covariance structure, followed by the heterogeneous autoregressive covariance structure, will be used. The first structure to yield convergence will be used for inference. The Kenward-Roger method will be used to estimate the denominator degrees of freedom. Type III sums of squares for the least-squares (LS) means will be used for the statistical comparison; the 95% confidence interval (CI) will also be reported. Unless otherwise specified, for MMRM, reported data from only planned visits will be used as the primary analysis.

Treatment comparisons of continuous efficacy, safety, and health outcome variables with a single postbaseline timepoint will be made using analysis of covariance (ANCOVA) with: (a) treatment group, and (b) baseline value in the model. Type III sums of squares for LS means will be used for statistical comparison between treatment groups. The LS mean difference, standard error, p-value, and 95% CI, unless otherwise specified, will also be reported. Missing data imputation method for the ANCOVA model is specified in Section 6.3.

Treatment comparisons for binary endpoints will be made using logistic regression with a Firth penalized likelihood (Firth 1993). The model will include the treatment groups. The Firth correction can be implemented in PROC Logistic by including 'firth' as an option in the model statement. The odds ratio and the corresponding CIs, as well as the treatment differences and the corresponding CIs, will be reported. If the number of observed events is less than 5 in any treatment arm an exact test (i.e., Fisher's exact) will be conducted instead of using a logistic regression.

The Kaplan-Meier (KM) product limit method will be used for time-to-event analyses. The hazard ratio and log-rank test will be reported. Time for all analyses will be described in units of days.

For all change from baseline analyses, patients who do not have a valid baseline measure will be excluded.

For Treatment Arms 12-14, all safety, efficacy, and health outcome endpoints will be summarized using descriptive statistics only.

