6.2. Adjustments for Covariates

Analyses may be adjusted for baseline values, where appropriate, however, analyses will not be adjusted for the stratification factor, duration since symptom onset (≤ 8 days vs. > 8 days).

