6.5. Multiple Comparisons/Multiplicity

Treatment Arms 1-8

As this is a Phase 2 (nonconfirmatory) dose-finding study; no adjustments for multiple comparisons will be made.

Treatment Arms 9-11

As this is a Phase 2 (nonconfirmatory) dose-finding study, no adjustments for multiple comparisons for the secondary endpoints will be made. However, a hierarchical multiple comparisons procedure, which will control type I error in the primary endpoint analysis, will be implemented. The primary endpoints will be tested in a sequential manner at a 1-sided 0.025 significance level. The following is a list of the primary outcomes to be tested:

- Primary (Test 1) LY3853113 in combination with LY3819253 and LY3832479 compared to placebo for the proportion of participants with SARS-CoV-2 viral load greater than 5.27 on Day 7
- Primary (Test 2) LY3853113 alone compared to placebo for the proportion of participants with SARS-CoV-2 viral load greater than 5.27 on Day 7

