6.10.1. Primary Outcome and Methodology

The primary endpoint is the proportion of participants with SARS-CoV-2 viral load greater than 5.27 on Day 7, corresponding to Ct value of less than 27.5 based on nasopharyngeal swab sampling for RT-PCR testing for SARS-CoV-2. Statistical hypotheses testing for the primary endpoint will be conducted using a logistic regression model at the two-sided 0.05 level.

The proportion of participants with SARS-CoV-2 viral load greater than 5.27 on Day 7 will be statistically analyzed using a logistic regression with a Firth penalized likelihood (Firth 1993). The Firth correction can be implemented in PROC Logistic by including 'firth' as an option in the model statement. The odds ratio and the corresponding CIs, as well as the treatment differences and the corresponding CIs, will be reported. If the number of observed events is less than 5 in any treatment arm an exact test (i.e. Fisher's exact) will be conducted instead of using a logistic regression.

If Day 7 SARS-CoV-2 viral load is missing, then Day 7 will be imputed using RSI as described in Section 6.3.4 for Treatment Arms 1-6 and LOCF described in Section 6.3.5 for Treatment Arms 7-13.

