6.10.2. Additional Analyses of the Primary Outcome

6.10.2.1. Bayesian Modeling

A Bayesian logistic regression model will be fitted to evaluate the success criteria by the Lilly statistics group with the model listed below:

$$\begin{aligned} r_{ij} \sim &Binomial(p_{ij}, 1) \\ &\log\left(\frac{p_{ij}}{1 - p_{ij}}\right) = \beta \times base_{ij} + \alpha_i \end{aligned}$$

Where,

 r_{ij} : is 0 if patient j on treatment i has a SARS-CoV-2 viral load greater than 5.27 on Day 7 and 1 otherwise

 $base_{ij}$: is the baseline viral load for patient j on treatment i

 β : a fixed coefficient on the covariate log base 10 baseline viral load

 α_i : a parameter corresponding to treatment i (with i=1 being the placebo group).

and priors:

$$\beta \sim N(0,100^2)$$

 $\alpha_1 \sim \pi(\alpha_1)$

At least 2 priors $(\pi(\alpha_1))$ will be considered for α_1 , a diffuse $N(0,100^2)$ and an informative prior based on available information at the time of analysis.

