6.10.3. Secondary Efficacy Analyses

6.10.3.1. SARS-CoV-2 Viral Load

6.10.3.1.1. Change from Baseline in SARS-CoV-2 Viral Load

Changes from baseline to Day 3, Day 5, Day 7, and Day 11 in SARS-CoV-2 viral load data in the log base 10 scale will be statistically analyzed using a linear mixed-effect model. The model will contain log base 10 transformed baseline as a covariate, treatment, day, treatment-by-day interaction) as fixed effects. The LS means and treatment differences (active treatment minus placebo) will be calculated and presented with their corresponding 95% CIs. In addition, the geometric mean ratio to baseline and corresponding standard error for each treatment, the ratio of geometric mean ratio to baseline vs placebo, and corresponding 95% CIs will be presented. All available data will be used in the analysis.

SARS-CoV-2 viral load, including changes from baseline, will be summarized and plotted by treatment and listed. Baseline is defined as the Day 1 predose assessment.

No imputations of missing data will be conducted.

6.10.3.1.2. SARS-CoV-2 Viral Load Among Participants Enrolled with ≤8 Days of Symptoms Prior to Randomization

Similar methodology, as described in Section 6.10.1, will be utilized on the subset of participants enrolled with ≤ 8 days of symptoms prior to randomization.

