6.16.2.11. SpO2 Measurements of Interest

The proportion of participants experiencing an SpO₂ measurement of interest (<96%, $\ge 96\%$), (<92%, $\ge 92\%$) through Day 11 and through Day 29 will be evaluated separately using a logistic regression analysis with treatment as a fixed effect and baseline SpO₂ as a covariate in the model. Missing values will be considered to be missing completely at random (MCAR).

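### The primary Day 7 test leaves out baseline viral load and the randomisation stratum: it is valid, but gives up some power

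*SAP*

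**What the plan says.** Two places in SAP 6.1.4 fix the model for binary endpoints. The methods table describes logistic regression as "Treatment comparisons of binary variables with treatment in the model", and the text on the Firth model says "The model will include the treatment groups". Section 6.10.1 applies that model to the primary endpoint ("Statistical hypotheses testing for the primary endpoint will be conducted using a logistic regression model") and names no covariate. In Arms 9-11 the same model carries a fixed sequence, combination first and LY3853113 alone second: "The primary endpoints will be tested in a sequential manner at a 1-sided 0.025 significance level" (6.5).

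The general covariate rule in 6.2 reads: "Analyses may be adjusted for baseline values, where appropriate, however, analyses will not be adjusted for the stratification factor, duration since symptom onset". That factor, at most 8 days versus more than 8 days, is the one used to stratify randomisation in 5.3.1.

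Elsewhere the SAP does adjust for baseline:

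- The Bayesian logistic model of this same Day 7 endpoint has "a fixed coefficient on the covariate log base 10 baseline viral load" (6.10.2.1), but as an additional analysis.
- The change-from-baseline model "will contain log base 10 transformed baseline as a covariate" (6.10.3.1.1), and the viral load AUC model in 6.10.3.1.3 and the ANCOVA default in 6.1.4 also include baseline.
- An exploratory binary SpO2 endpoint is analysed "using a logistic regression analysis with treatment as a fixed effect and baseline" SpO2 (6.16.2.11), so a binary outcome is not in itself the reason for leaving baseline out.

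**The concern.** Baseline viral load is a natural predictor of whether viral load is still high a week later, and it is already collected. The SAP treats it as a covariate everywhere except in the model that carries the hypothesis tests, and gives no reason. Under the LOCF rule in 6.3.5, a participant with no post-baseline value before a missing Day 7 has the baseline value carried into the outcome, which ties the two together further. The SAP also treats time since onset as related to viral load: 6.16.2.12 adjusts plotted values by 0.158 per day from symptom onset. Yet 6.2 bars the stratum built on that variable.

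Bias and type I error are not in question. At stake are power and the precision of the risk difference. This matters most in Arms 9-11, where the second comparison counts only if the first succeeds, so a gain on each test has a larger effect on the chance that both succeed.

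**Working it through.** **Inputs from the SAP.** Arms 9-11: 122 per arm, 28% placebo versus 12% active, stated power about 84% (5.2). Arms 7-8: 100 per arm, 19% versus 5%, stated power greater than 87% (5.2). Two-sided 0.05, or one-sided 0.025 in the sequence; both use a critical value of 1.96. Fisher's exact test replaces the model if any arm has fewer than 5 events (6.10.1).

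**Reproducing the stated power, Arms 9-11.** The mean proportion is 0.20.

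- Null SE = √(2 × 0.20 × 0.80 / 122) = 0.0512.
- Alternative SE = √((0.28 × 0.72 + 0.12 × 0.88) / 122) = 0.0502.
- Without continuity correction: z = (0.16 − 1.96 × 0.0512) / 0.0502 = 1.19, power 88.3%.
- With continuity correction (subtract 1/122 = 0.0082 from the difference): z = 1.02, power 84.7%.
- Fisher's exact test throughout, by enumeration: 85.4%.

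The stated figure therefore matches a continuity-corrected or Fisher calculation. The planned rule (Firth, with Fisher below 5 events) has exact power of 87.9% in Arms 9-11 and 86.7% in Arms 7-8.

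**Effect of adjustment.** The SAP gives no baseline-to-Day 7 association, so these are assumptions: correlation 0 to 0.6, 25% of participants in the >8-day stratum, and a Day 7 stratum shift of 0 to 0.5 SD. Day 7 viral load was simulated as latent normal and allocation was balanced within stratum. Arms 9-11 shared one placebo arm and one joint model. Tests were Firth Wald tests with the Fisher rule kept, in 8,000 trials per scenario. The Monte Carlo standard error of one power figure is √(0.88 × 0.12 / 8000), about 0.4 points; differences between models fitted to the same trials are more precise. Unadjusted power was 87.5-88.9% (Arms 9-11), 80.1-81.2% for both sequential tests, and 86.5-87.5% (Arms 7-8).

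| Assumed correlation | 0 | 0.15 | 0.3 | 0.45 | 0.6 |
|---|---|---|---|---|---|
| Arms 9-11, one test, baseline added (points) | 0 | +0.4 to 0.5 | +1.2 to 1.5 | +3.0 to 3.3 | +5.5 to 5.9 |
| Arms 9-11, one test, baseline and stratum added (points) | −0.1 to +0.5 | +0.5 to 0.9 | +1.3 to 1.9 | +3.3 to 3.9 | +6.0 to 6.2 |
| Arms 9-11, both tests succeed, baseline added (points) | −0.1 to +0.2 | +0.4 to 0.8 | +2.0 to 2.2 | +4.8 | +8.6 to 8.8 |
| Arms 7-8, baseline added (points) | −0.2 to −0.1 | 0 to +0.1 | +0.7 to 1.1 | +2.1 to 2.4 | +3.7 to 4.6 |
| SD of standardised risk difference relative to unadjusted, Arms 9-11 | 1.00 | 0.995 | 0.98 | 0.95 | 0.89-0.91 |
| Mean SE of log odds ratio, Arms 9-11 (0.347 unadjusted) | 0.348 | 0.350 | 0.356 | 0.369 | 0.392 |

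A risk-difference SD ratio of 0.95 is worth about 1/0.95² − 1 = 11% more participants. The odds-ratio interval widens because the conditional odds ratio lies further from 1 and has a larger standard error; the power gain comes from the larger effect on that scale.

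A second simulation assumed a log odds ratio per SD of baseline instead of a correlation. For values of 0, 0.5, 1.0, 1.5 and 2.0, adding baseline raised power in Arms 9-11 by about 0, 1, 4, 6.5 and 9 points.

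**Stratum alone.** In Arms 9-11 it adds 0 to 0.8 points, or up to about 1.5 with 40% in the >8-day stratum and a log odds ratio of −1.5. In Arms 7-8 it adds 0.3 to 0.5 points, of which 0.4 appears even with no stratum effect.

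**Type I error.** At 122 per arm: 4.5-4.7% unadjusted, 4.6-4.9% with both covariates. At 100 per arm: 4.0-4.3% and 4.2-4.5%.

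**Fisher rule.** The probability of fewer than 5 events in an active arm is 0.07% at 12% of 122, but 43.6% at 5% of 100. This is why the gain in Arms 7-8 is smaller.

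**Missing baseline.** With correlation 0.45 and shift 0.3, replacing missing baselines by the pooled mean gave a gain of +3.0 points with none missing, +3.4 with 5% missing and +3.0 with 10% missing.

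**The case against.** The strongest reply is that nothing here is an error. The test is valid, prespecified, and more powerful than the SAP claims for Arms 9-11. The sections do not contradict one another, and 6.5 calls the study nonconfirmatory. Baseline-adjusted evidence will also exist, from the Bayesian model and the change-from-baseline model. All of that is correct, and it limits the point to efficiency. It does not explain why the model that decides success should omit a covariate the SAP itself uses for the same endpoint.

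The gain rests on an assumed correlation. That also stands: at 0.15 or less it is under 1 point, and 6 points is the end of the assumed range, not a limit. The stratum contributes little; the reason to include it is that it was used to randomise, not the power it brings.

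Adjustment makes the odds ratio conditional and widens its interval, and the Fisher rule cannot carry a covariate, so in Arms 7-8 the event count would often decide whether the test is adjusted. These are real costs. The first is met by reporting a standardised risk difference. The second barely arises in Arms 9-11 at the design rates.

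Two practical points remain open. Section 6.1.4 requires an amendment if a change alters a principal feature of the protocol, and the protocol is not at hand. The SAP also does not say whether treatment-coded Day 7 data from Arms 9-11 had been seen when Version 10 was approved.

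**Conclusion.** The point holds as a matter of efficiency. The primary hypothesis tests rest on a treatment-only model, although baseline viral load is collected, permitted by 6.2 and used in the additional model of the same endpoint. For an assumed baseline-to-Day 7 correlation of 0 to 0.6, the forgone power in Arms 9-11 is about 0 to 6 points for one test and about 0 to 9 points for success on both; in Arms 7-8 it is about 0 to 5 points. Nearly all of it comes from baseline viral load. No conclusion drawn from the planned test would be invalid. The change is worth making because it costs little and loses essentially nothing if the correlation is near zero, but the trial does not depend on it.

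**What to change.** 1. In 6.2, remove the exclusion of the symptom-duration stratum.
2. In 6.1.4 and 6.10.1, for placebo-controlled arms whose treatment-coded Day 7 data have not been seen (chiefly Arms 9-11), specify the Firth model with treatment, baseline log10 viral load and the ≤8/>8-day stratum. Leave the Fisher rule for fewer than 5 events as it is.
3. Replace a missing baseline by the mean of observed baselines pooled over arms, so that nobody is dropped.
4. Report the odds ratio, labelled conditional, and a standardised risk difference with its confidence interval. Keep the unadjusted analysis as a sensitivity analysis.
5. For Arms 1-6, where the revision history for Version 7 records post hoc analyses, add the adjusted model as a sensitivity analysis only. Do the same for Arms 7-8 if the early primary analysis allowed by 6.15.1 has been done.

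The cost is SAP wording and minor programming, with no new participants or data. The sponsor should check whether the protocol describes the primary model in terms that would require an amendment. The adjusted odds ratio will not be directly comparable with the unadjusted one; the standardised risk difference keeps the marginal scale.

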6.2. Adjustments for Covariates

Analyses may be adjusted for baseline values, where appropriate, however, analyses will not be adjusted for the stratification factor, duration since symptom onset (≤ 8 days vs. > 8 days).

6.3. Handling of Dropouts or Missing Data

The SoA, outlined in the protocol, specifies the allowable windows for assessments. Assessments performed outside these windows will not be excluded from any analysis but may be reported as a protocol deviation (see Section 6.14).

6.3.1. Modified Non-Responder Imputation

For analysis of viral clearance (yes/no), missing data will be imputed using a mNRI. Specifically, for patients that have missing postbaseline data for reverse transcription polymerase chain reaction (RT-PCR) testing for SARS-CoV-2 (based on nasopharyngeal swab sampling) then viral clearance status will be imputed as follows:

- If a participant has previously achieved viral clearance (i.e. the participant previously had 2 consecutive negative tests), then viral clearance will be imputed as "Yes".
- If a participant has not previously achieved viral clearance (i.e. the participant does not have 2 consecutive previous negative tests), then viral clearance will be imputed as "No".

After imputation, data from all participants will be included in the analyses. The application of mNRI to viral clearance helps ensure that the maximum number of randomized participants.

6.3.2. Mixed-Effects Model Repeated Measures

For continuous variables, the primary analysis will be MMRM with the MAR assumption for handling missing data. This analysis considers both missingness of data and the correlation of the repeated measurements. No additional imputation methods will be applied to the MMRM analysis.

For all change from baseline analyses, patients who do not have a valid baseline measure will be excluded from the model.

6.3.3. Highest Disease States Imputation

For the analyses related to National Institute of Allergy and Infectious Diseases (NIAID)/World Health Organization (WHO) ordinal scales, the following imputation will be considered if applicable.

For participants whose data is missing during the hospitalization period (not yet recovered), a score of 2, which is the highest value for a hospitalization status, will be used for imputation.

For participants whose data is missing after recovery or discharged, a score of 7, the highest value for a recovery or nonhospitalized status, will be used for imputation.

